## 1.2 BACKGROUND ON R07062931

RO7062931 is a N-Acetylgalactosamine (GalNAc)-targeted locked nucleic acid (LNA)-containing single stranded oligodeoxyribonucleotide (SSO), complementary to HBV genome-derived mRNA species, intended for the treatment of CHB infections. Chronicity in CHB is believed to be perpetuated, at least in part, by protein products expressed from the HBV genome which are derived from translation of four mRNA species transcribed from the cccDNA template located in the nucleus of infected hepatocytes.

See the RO7062931 Investigator Brochure (IB) for details on non-clinical and clinical studies.

### 1.2.1 Previous Non-Clinical Studies

RO7062931 has shown potent antiviral activity through the inhibition of [REDACTED], [REDACTED]. RO7062931 is [REDACTED] active in vitro against [REDACTED]. In mice infected with a recombinant adeno-associated virus (AAV) carrying a replicable HBV genome (AAV-HBV), administration of RO7062931 reduced [REDACTED]

### **1.2.2 Previous Clinical Studies**

Study BP39405, the first-in-human (FIH) study with RO7062931, was initiated in January 2017. In this ongoing study, as of 8 November, 2017, 60 healthy subjects (including 15 Asian healthy subjects) had received a single dose of RO7062931 or placebo at various dose levels from 0.1, 0.3, 1.0, 2.0, 3.0 to 4.0 mg/kg. As of 8th November 2017, two HBV patients had been randomized in Part 2a of the study.

## **1.3 STUDY RATIONALE AND BENEFIT–RISK ASSESSMENT**

### **1.3.1 Study Rationale**

Study BP39405 is the first clinical study with RO7062931 designed to assess: the safety, tolerability and pharmacokinetics (PK) of subcutaneously administered single ascending doses (SAD) in healthy volunteers (HVs; Part 1); and safety, tolerability, PK, and pharmacodynamic (PD) effects of subcutaneously administered multiple doses to CHB patients (Part 2). Study YP39432 will assess the safety, tolerability and PK of single

doses of RO7062931 in healthy Chinese volunteers. This initial evaluation will be important to inform future clinical studies in Chinese subjects.

[REDACTED]

[REDACTED]

[REDACTED]

This study will be conducted in healthy Chinese volunteers and results from this study will be compared with the global study, BP39405, to determine if there may be any detectable differences between Caucasian and Asian healthy volunteers in safety, tolerability and pharmacokinetics. For the healthy volunteers, no therapeutic benefit is anticipated. However, data from these healthy volunteers is expected to provide a clearer and more consistent assessment of safety and PK to allow better design of therapeutic studies in HBV patients.

### **1.3.2        Benefit–Risk Assessment**

*Limited* clinical experience with RO7062931 currently exists. The evaluation of the potential risks of drug administration and the specific tests, observations, and precautions required for this clinical study with RO7062931 will be based on information from non-clinical toxicology and safety pharmacology studies as well as available data from the FIH study BP39405. Safety and tolerability will be carefully assessed, and HVs will be closely monitored. All dose levels to be included in this study will be within the dose-range which has been demonstrated to be safe and well-tolerated in the FIH study (BP39405). The study will be done under a controlled setting, with tight clinical and laboratory monitoring to minimize potential risks to the participants. Dose-escalation

decisions will be made based on the safety/tolerability and PK observations from the previous cohorts and the ongoing study BP39405.

## **2. OBJECTIVES**

### **2.1 PRIMARY OBJECTIVES**

The primary objective of this study is:

- To assess the safety and tolerability of RO7062931 compared to placebo after single-ascending doses in healthy Chinese volunteers.

### **2.2 SECONDARY OBJECTIVES**

The secondary objective for this study is:

- To assess plasma and urine PK of RO7062931 and, if applicable metabolite(s), after single-ascending doses in healthy Chinese volunteers.

## **3. STUDY DESIGN**

[figure not shown]
### **3.1 DESCRIPTION OF STUDY**

#### **3.1.1 Overview of Study Design**

This study is randomized, Sponsor-open, Investigator-blind and subject-blind. Up to *five* ascending dose-levels (cohorts) will be explored within the dose-range shown to be safe and well-tolerated in Study BP39405. The planned doses for the first *four* cohorts will be 0.3 mg/kg, 1.0 mg/kg, 2.0 mg/kg and 3.0 mg/kg, respectively (see [Figure 1](#)). The planned dose-levels may be modified and an additional (optional, 4.0 mg/kg) cohort enrolled based on emerging results from ongoing preclinical and clinical studies (including this study).

It is planned to enroll 10 HVs in each cohort; eight HVs will receive RO7062931 and two will receive placebo. Sentinel dosing will be employed in each cohort, where two subjects will be dosed on Day 1, of which at least one HV will receive RO7062931 in order to monitor *for potential* acute reactions. The remaining 8 subjects will be dosed on the following day (24 hours after the initial administrations) following satisfactory safety assessment of the first two HVs by the Investigator. The sentinel dosing requirements may be modified based on the data from Study BP39405.

**Figure 1 Study Design**

The total duration of the study for each HV will be up to 16 weeks divided as follows:

- Screening: Up to 4 weeks;
- In-Clinic period: Days -1 to 3;
- Safety Follow-up: up to at least Day 85

### **3.1.2 Dose- Escalation Decisions**

Dose-escalation/review meetings will be conducted by the Investigator, the Medical Monitor, and the Sponsor Clinical Team prior to each RO7062931 dose-escalation (see Section 3.1.2.1). The actual doses may be modified based on emerging data from this study, and emerging results from ongoing preclinical studies and Study BP39405.

Escalation to the next dose cohort will be based primarily on the review of safety and tolerability information (including adverse events, electrocardiograms [ECGs], vital signs, clinical laboratory test results) collected *up to 28 days post-dose (Day 29 ± 2 Days)* and, all available PK data collected at least 7 days post-dose in a minimum of 8 subjects (receiving active drug or placebo) within the previous cohort. The decision to escalate the dose will be made by mutual agreement between the Sponsor and the Investigator.

#### **3.1.2.1 Dose-Escalation Decision Criteria**

This study uses a dose-escalation schedule that may be modified if:

- Events emerge that the Sponsor and/or Investigator consider indicators that the planned dose-escalation step would result in unacceptable risks for the safety of the HVs.

- The Sponsor and Investigator agree to do so and neither considers that the proposed subsequent dose level poses an unacceptable risk to the study subjects.

Single doses will not be escalated if the dose-escalation stopping criteria are met (see Section 3.1.2.2 below) but may exceed the dose level of 4.0 mg/kg (see Section 3.2.1) only if anticipated to be safe and necessary to generate additional PK data in support of dosing regimens for use in patients.

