### **STUDY DESIGN**

#### **Description of Study**

This study is randomized, Sponsor-open, Investigator-blind and subject-blind. *Up to five ascending dose-levels (cohorts) will be explored within the dose-range shown to be safe and well-tolerated in Study BP39405.* The planned doses for the first four cohorts will be 0.3 mg/kg, 1.0 mg/kg, 2.0 mg/kg and 3.0 mg/kg, respectively (see Figure 1). The planned dose-levels may be modified and an additional (optional, 4.0 mg/kg) cohort enrolled based on emerging results from ongoing preclinical and clinical studies (including this study).

*It is planned to enroll 10 healthy volunteers (HVs) in each cohort; eight HVs will receive RO7062931 and two will receive placebo. Sentinel dosing will be employed in each cohort, where two subjects will be dosed on Day 1, of which at least one HV will receive RO7062931 in order to monitor for potential acute reactions. The remaining 8 subjects will be dosed on the following day (24 hours after the initial administrations) following satisfactory safety assessment of the first two HVs by the Investigator. The sentinel dosing requirements may be modified based on the data from Study BP39405.*

---

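### Section 3.1.2.1 would allow a single dose above 4.0 mg/kg on expected safety alone, a weaker test than the protocol's commitment to stay within the range already shown safe in BP39405

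*Combined protocol and SAP*

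**What the plan says.** Section 3.1.2.1, after barring escalation when the stopping criteria are met, adds that single doses "may exceed the dose level of 4.0 mg/kg (see Section 3.2.1) only if anticipated to be safe and necessary to generate additional PK data"; the stated purpose is to guide how patients are later dosed. The sentence does not mention BP39405 and gives no upper limit or maximum step above 4.0 mg/kg.

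Elsewhere the protocol ties its doses to BP39405:

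- Synopsis, Description of Study: "Up to five ascending dose-levels (cohorts) will be explored within the dose-range shown to be safe and well-tolerated in Study BP39405".
- Section 1.3.2, referring to BP39405: "All dose levels to be included in this study will be within the dose-range which has been demonstrated to be safe and well-tolerated".
- Section 3.1.1: the dose levels "will be explored within the dose-range shown to be safe and well-tolerated in Study BP39405".
- Section 3.2.1 repeats the commitment of Section 1.3.2 for all dose levels.
- Section 3.2.2 says the doses will already have been declared safe in BP39405.

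On what BP39405 covers, Section 1.2.2 reports that, as of 8 November 2017, healthy subjects had received a single "dose of RO7062931 or placebo at various dose levels from 0.1, 0.3, 1.0, 2.0, 3.0 to 4.0 mg/kg". Section 3.2.1 describes single doses from 0.1 to 4.0 mg/kg as considered safe and well tolerated. The optional fifth cohort is specified as 4.0 mg/kg.

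**The concern.** The rule and the commitment use different kinds of test. *Anticipated* is a forecast. *Shown*, *demonstrated* and *declared* require results already in hand. Section 3.1.2.1 is what the escalation meeting applies, and a permission to go above 4.0 mg/kg can be taken as an exception to the general limit.

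Section 1.3.1 states: "For the healthy volunteers, no therapeutic benefit is anticipated". With no benefit to the volunteers, the benefit-risk case in Section 1.3.2 leans on every dose having prior human safety data. If the operative rule can be met without such data, that case does not cover everything the protocol permits.

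The top of the range is also where prior data matter most. Section 3.2.4 notes acute renal tubular toxicity at the highest dose tested in a first-in-human study of another LNA antisense oligonucleotide, and raised kidney markers in the rat and monkey studies of RO7062931.

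**Working it through.** No sample size, power or error rate is involved. The check compares the rule with the other current protocol text.

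**Step 1: the test each place applies.**

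| Place | Test | Tied to BP39405? |
|---|---|---|
| Synopsis, Description of Study | shown | yes |
| Section 1.3.2 | demonstrated | yes |
| Section 3.1.1 | shown | yes |
| Section 3.2.1 | demonstrated | yes |
| Section 3.2.2 | declared | yes |
| Section 3.1.2.1 (the rule) | anticipated, and needed for PK | not in the sentence itself |

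Shown 2 + demonstrated 2 + declared 1 = 5 statements with a completed test. The rule alone uses a forecast.

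**Step 2: what the completed test covers.** Section 1.2.2 lists six BP39405 levels: 0.1, 0.3, 1.0, 2.0, 3.0 and 4.0 mg/kg. The maximum is 4.0 mg/kg, matching Section 3.2.1. On the data in this protocol, any dose above 4.0 mg/kg could satisfy Section 3.1.2.1 while failing all five statements.

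**Step 3: whether another safeguard supplies the missing condition.**

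- *Mutual agreement* (Sections 3.1.2 and 3.1.2.1): Sponsor and Investigator must agree, and neither may see unacceptable risk. This is judgement, with no stated data requirement at the new dose.
- *Day 29 review* (Section 3.1.2): this looks at the previous, lower-dose cohort.
- *Sentinel dosing* (Section 3.1.1): "Sentinel dosing will be employed in each cohort, where two subjects will be dosed on Day 1". Under Section 4.3 one of the two receives active drug. The other eight (7 active, 1 placebo) follow 24 hours later if the Investigator is satisfied. This uses the study's own data, and the requirement may itself be modified.
- *Stopping criteria and related-SAE halt* (Section 3.1.2.2): these act after exposure, for example when more than 2 of 8 active subjects at a dose level have a qualifying event.

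Safeguards requiring BP39405 data at the proposed dose: 0 of 4.

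**Step 4: other references to BP39405 in escalation.** Section 3.1.2 names it as one of three sources for modifying a dose, with this study and preclinical work. Section 1.3.2 says dose-escalation "decisions will be made based on the safety/tolerability and PK observations from the previous cohorts and the ongoing study BP39405". Both make BP39405 an input. Neither makes data at the proposed dose a condition.

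**Step 5: exposure.** Cohorts planned above 4.0 mg/kg: 0, so planned active exposure affected is 0. If one were opened at the cohort size in Section 6.1, active exposure would be 8 (1 sentinel + 7 others).

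**The case against.** The strongest reply is that nothing is missing. The rule sets necessary conditions and waives none. It cites Section 3.2.1, which states the BP39405 limit, and the meeting is bound by the whole protocol. BP39405 is also ongoing, so a dose above 4.0 mg/kg could later satisfy both texts. This reading is available, which is why the point is a mismatch of tests and not a flat contradiction. But the readable text of Section 3.2.1 supports doses only up to 4.0 mg/kg, while the rule exists to go beyond that. A reader could take it as an exception, and a healthy-volunteer dosing rule should not depend on which reading prevails.

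Section 3.2.1 also uses *anticipated* of doses up to 4.0 mg/kg, which already have BP39405 data. That softens the contrast in wording, but the sentence is not one of the five within-range commitments and says nothing about higher doses.

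Part of Section 3.2.1 is redacted and may address doses above 4.0 mg/kg. That cannot be excluded. The visible within-range sentence, however, carries no exception.

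Finally, the study is limited to five cohorts and 50 volunteers, so a higher dose would have to replace a planned level or the limit would have to change. The 3.0 and 4.0 mg/kg cohorts were themselves added by substantial amendment, and Section 9.5 requires ethics approval for such amendments. This suggests a higher dose might get ethics review, but does not establish it: Sections 3.1.1 and 3.1.2 let dose levels be modified, and Section 3.1.2.1 already contains the permission. These points bear on how likely the situation is. They do not add the condition.

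**Conclusion.** The concern holds. One operative rule applies a weaker test than five statements elsewhere in the protocol, and none of the four other safeguards requires BP39405 safety data at the proposed dose. It should be corrected because the benefit-risk statement for healthy volunteers depends on that condition.

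The practical size is modest. No planned dose is affected. Harm would require both parties to agree a dose above the planned maximum ahead of BP39405 data, and the figure of 8 active volunteers is hypothetical. No endpoint or analysis changes.

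The conclusion rests on a literal reading of Section 3.1.2.1, on the BP39405 range as reported at 8 November 2017 (a data position, not a protocol ceiling), and on the readable part of Section 3.2.1. Confidence is medium for the last reason.

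**What to change.** Reword the permission in Section 3.1.2.1 so that a single dose above 4.0 mg/kg needs all three of the following: BP39405 has already established safety and tolerability at that dose, the dose is expected to be safe in this Chinese population, and the further PK data are needed. This keeps the option to go higher and brings the rule into line with the Synopsis and Sections 1.3.2, 3.1.1, 3.2.1 and 3.2.2. The sponsor should check the redacted part of Section 3.2.1 for consistency, since it cannot be verified here.

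The cost is one sentence, with no added subjects or procedures. The downside is that a dose above 4.0 mg/kg must wait for BP39405 safety data at that level, which Sections 1.3.2 and 3.2.2 already lead the reader to expect.

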### **3.1.2.2 Dose-Escalation Stopping Criteria**

Dose-escalation will not be implemented as planned if one of the criteria below is fulfilled, unless it is obvious that the occurrence is not considered to be related to RO7062931.

Dose-escalation will be stopped if at a dose level, more than 2 of 8 HVs receiving RO7062931 experience the following:

- Severe or clinically significant (as defined by the Investigator) RO7062931-related adverse events of the same character, or
- Clinically significant RO7062931-related laboratory abnormality of the same character, or
- Clinically significant RO7062931-related changes in vital signs or ECGs of the same character (e.g., QTcF > 500 msec, or > 60 msec longer than the pre-dose baseline, within the first 48 hours post-dose).
- Within two consecutive dose cohorts, four occurrences (in 4 HVs) of any of the above conditions in HVs receiving active drug.
- Other findings (regardless of the incidence rates) that at the joint discretion of the Sponsor and the Investigator indicate that dose-escalation should be halted.

Additionally, planned dose-escalation may be stopped by mutual agreement between the Sponsor and Investigator, [REDACTED]

In case the dose-escalation is stopped, lower doses within the tolerated dose-range could be investigated or a dose repeated in the subsequent cohorts by mutual agreement between the Sponsor and Investigator, in order to increase the amount of data within this tolerated dose-range.

*Any serious adverse event considered related to study drug will lead to an immediate halt of study drug dosing, dose escalation and enrollment of new subjects until a thorough investigation has been conducted by the Sponsor's Clinical Team and the Principal Investigator. The sponsor or designee will notify all investigators and IRBs/EC regarding the outcome of such investigation, and the study will only continue if agreed by the IRBs/EC.*

Due to the exploratory nature of this clinical study, its conduct can be discontinued at any time at the discretion of the Sponsor (see Section 4.7).

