## **4.2 STUDY POPULATION**

Healthy volunteers must satisfy all inclusion and exclusion criteria to be enrolled into the study. Under no circumstances are subjects who enroll in this study permitted to be re-randomized to another cohort of this study.

Study subjects who drop out of the study for non-safety reasons may be replaced to ensure sufficient data to characterize the safety, tolerability, and PK and/or to make dose-escalation decisions. Study subjects who withdraw from the study due to poor tolerability or for study drug-related adverse events will not be replaced.

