#### **4.3 METHOD OF TREATMENT ASSIGNMENT AND BLINDING**

This study is Sponsor-open, Investigator-blinded and subject-blinded. This means that the study subjects will be blinded, the Investigator(s), site staff observing the subjects will be blinded and the Sponsor will be unblinded. Additionally, the site pharmacist and the study drug administrator will be unblinded. Members of the Sponsor's study team who do not have direct contact with the Investigator or study site staff will be unblinded. This does not include any Contract Research Organisations (CROs) and any Sponsor staff in direct contact with the Investigators and the study sites, who will remain blinded.

Ten HVs will be randomized to active drug or placebo in each dose cohort/level in a 4:1 ratio. The randomization numbers will be generated by the Sponsor or its designee. The randomized treatment assignment will be allocated from the list sequentially to subjects in the order in which they are enrolled. For each dose cohort, the randomization will be designed such that of the first 2 HVs, one will receive active drug, and the other will receive placebo. The remaining 8 HVs in the cohort will be randomized such that 7 receive active drug and 1 receives placebo. The treatment allocation will be managed by the unblinded Pharmacist and will be based on the randomization assignment list. An unblinded study drug administrator will administer the drug to the subject. Drug administration to a subject will be performed in isolation of other subjects.

To allow informed recommendations or decisions regarding the dose selection, an integrated assessment of the safety, tolerability and available PK data will be made prior to each dose decision (see Sections [3.1.2](#) to [3.1.3](#)). If required, unblinded data (individual as well as at group level) may also be presented to the Drug Safety Committee or other experts of the Sponsor.

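### Does the stopping threshold of more than 2 in 8 lose its meaning if fewer than 8 volunteers on RO7062931 are available at the escalation review?

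*Combined protocol and SAP*

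**What the plan says.** Each cohort has a fixed composition (Section 3.1.1): "It is planned to enroll 10 HVs in each cohort; eight HVs will receive RO7062931 and two will receive placebo". Section 4.3 builds this from a sentinel pair (1 active, 1 placebo) and a remaining group of 8 (7 active, 1 placebo).

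The per-dose-level criterion in Section 3.1.2.2 is: "Dose-escalation will be stopped if at a dose level, more than 2 of 8 HVs receiving RO7062931 experience the following". A second criterion covers two consecutive cohorts and has no denominator: "four occurrences (in 4 HVs) of any of the above conditions in HVs receiving active drug". The same section adds a stop at joint discretion whatever the incidence, and an immediate halt for any related serious adverse event. Part of one sentence there, on stopping by mutual agreement, is redacted and is not counted as missing.

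Section 3.1.2 bases escalation on safety information up to Day 29 and on available PK data "in a minimum of 8 subjects (receiving active drug or placebo) within the previous cohort". It requires the Sponsor and the Investigator to agree before the dose is raised.

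Section 4.2 makes replacement optional for dropouts unrelated to safety, and excludes it otherwise: "Study subjects who withdraw from the study due to poor tolerability or for study drug-related adverse events will not be replaced".

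On blinding, Section 4.3 leaves part of the Sponsor's team unblinded. It keeps the Investigator blinded, and likewise CROs and "any Sponsor staff in direct contact with the Investigators and the study sites, who will remain blinded". If needed, "unblinded data (individual as well as at group level) may also be presented to the Drug Safety Committee or other experts of the Sponsor".

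**The concern.** Read together, Sections 3.1.2 and 3.1.2.2 seem to use different denominators. The threshold assumes 8 volunteers on active drug, while the review minimum counts 8 subjects of either arm. With 2 placebo subjects in a cohort, 8 reviewed subjects may include only 6 or 7 on RO7062931, and no sentence says how the threshold then applies. If it is a count, 3 events are still needed. If it is a proportion above 2/8, two events are enough. The same data could then trigger the automatic stop or not, depending on a reading that nobody fixed in advance. Optional replacement does not guarantee 8.

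A second worry is that both numerical criteria need the allocation. The Investigator is blinded yet must agree to escalate, and no passage says who counts events in the active arm or in what form the answer reaches the meeting. If individual allocations came out there, the Investigator would go on judging causality with that knowledge until the Day 85 visit.

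At stake would be the strength of a pre-specified safety rule, and the blinding of the person who assesses adverse events.

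**Working it through.** **Plan's own figures.** At 4:1, 10 × 4/5 = 8 active per cohort. The sentinel scheme gives 1 + 7 = 8 active and 1 + 1 = 2 placebo. Five cohorts of 10 give 50. All agree with Sections 4.3 and 6.1. The documents state no event rate, alpha or power, so every rate below is an assumption.

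**How many active among 8 reviewed.** If the two unreviewed subjects are a random pair from the 10:
- 6 active: C(8,6)·C(2,2)/C(10,8) = 28/45 = 62.2%
- 7 active: 8·2/45 = 16/45 = 35.6%
- 8 active: 1/45 = 2.2%

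So if the minimum really governed the safety review and only 8 subjects were reviewed, a short active arm would be usual.

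**Where the readings part.** More than 2 of 8 means above 25%. Two events are 2/7 = 28.6% or 2/6 = 33.3%. The readings therefore differ only at exactly 2 events in 7 or 6. With 8 in the denominator they are identical (3 or more).

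**Chance that the per-dose-level criterion is met.** With X ~ Bin(n, p), the count reading is P(X ≥ 3) and the proportion reading for n = 7 or 6 is P(X ≥ 2).

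| Assumed rate | Count, n = 8 / 7 / 6 | Proportion, n = 7 / 6 | Exactly 2 events, n = 7 / 6 |
|---|---|---|---|
| 10% | 3.8% / 2.6% / 1.6% | 15.0% / 11.4% | 12.4% / 9.8% |
| 20% | 20.3% / 14.8% / 9.9% | 42.3% / 34.5% | 27.5% / 24.6% |
| 30% | 44.8% / 35.3% / 25.6% | 67.1% / 58.0% | 31.8% / 32.4% |
| 50% | 85.5% / 77.3% / 65.6% | 93.8% / 89.1% | 16.4% / 23.4% |

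**Adding the two-cohort criterion.** Let the previous cohort be x1 ~ Bin(8, 0.10), given x1 ≤ 2. Stop if the current cohort meets its own threshold or if the two cohorts together reach 4. At a 30% current rate this gives 49.4% with 8 active. With 7 active it gives 40.2% (count) or 67.1% (proportion), and with 6 active 30.6% or 58.0%.

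All these figures are conditional on having 6 or 7 active. They treat the missing volunteers as contributing no events.

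**How likely that condition is, from the text.**
1. In Section 3.1.2 the safety information has its own time limit (Day 29). The minimum of 8 follows the PK clause, with its separate limit of at least 7 days, and most naturally belongs to it. On that reading a PK data requirement and a safety threshold serve different purposes and do not conflict. What remains is that no safety minimum is stated.
2. Section 3.1.3 places the review after the cohort has been completed.
3. The threshold counts volunteers who receive RO7062931. There is one injection, so anyone who leaves afterwards has received it and events already seen count. Section 6.3.1 likewise keeps every dosed volunteer in the safety population, withdrawn or not. With 8 dosed, the denominator is 8 and the two readings coincide.
4. Withdrawals that will not be replaced are those for poor tolerability or drug-related events. They are the events that the rule looks for, so they feed the numerator.
5. What is left is a cohort with fewer than 8 active volunteers dosed, or an active volunteer lost early for a reason unrelated to safety and not replaced. Section 4.2 allows replacement expressly to support escalation decisions.

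**The case for a change.** The strongest reply is that a stopping rule should not depend on a charitable reading. The mention of either arm in Section 3.1.2 shows that incomplete cohorts were foreseen. If the minimum is for PK only, the safety review has no minimum at all. One unevaluable active volunteer is enough to create the ambiguity, and the two-cohort criterion does not remove it: at a 30% rate with 7 active, the readings still give 40% and 67%. The arithmetic stands, and so does the statement that no visible sentence settles the case below 8.

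It does not follow that the rule fails. Section 3.1.2.2 is written in counts throughout (more than 2, then four volunteers), and no percentage appears. The proportion reading has to be supplied from outside. Exactly 2 events in 6 or 7 also does not commit anyone to escalate. Joint discretion can halt at any incidence, Section 3.1.2.1 lets either party's view of unacceptable risk change the schedule, and agreement of both parties is needed to go up. The divergence concerns only the automatic trigger.

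On who counts, it is true that no one is named. But the study is Sponsor-open, unblinded Sponsor members exist, Section 4.3 gives a route for unblinded data, and Section 3.1.3 has the decisions documented in writing. No passage sends individual allocations to the Investigator, so the feared unblinding is conjecture.

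**Conclusion.** No change to the plan is needed. The mismatch between the two uses of 8 is real on the page, but it is a missing detail in an uncommon case. Followed as written, the rule can be applied: three or more volunteers on active drug with a qualifying event of the same character meet the criterion.

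If the uncommon case arose, the reading would matter. At an assumed 30% rate, the chance of an automatic stop with 7 active is 35% (count) or 67% (proportion), against 45% with 8. At 10% it is 2.6% or 15.0%, against 3.8%. The documents give no event rate and no dropout rate, so the unconditional effect cannot be computed. Section 3.2.1 describes single doses of 0.1 to 4.0 mg/kg as considered safe and well tolerated, which makes the higher assumed rates less plausible.

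The conclusion rests on three points of reading: the minimum of 8 attaches to the PK data, a dosed volunteer stays in the denominator after leaving, and the threshold is a count as worded. It also rests on the remaining protections in Sections 3.1.2 to 3.1.2.2 being used. Whether a different threshold would suit a smaller active arm is a clinical matter on which this review takes no position.
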